Date

Protocol Synopsis

Full Title	A Multi-Center, Prospective, Randomized Study Comparing Removable, Self-Expanding Metal Stents to Plastic Stents for the Treatment of Benign Biliary Strictures Secondary to Chronic Pancreatitis
Short Title	WallFlex Biliary FC Chronic Pancreatitis RCT
Primary Objective	To compare the use of Self Expanding Metal Stents (SEMS) to plastic stents for the treatment of benign biliary strictures secondary to chronic pancreatitis as it pertains to stricture resolution rates, complication rates and number of ERCP procedures during 24 months.
Study Devices	
Group A: Metal Stents – MS Arm WallFlex™ Biliary RX Fully Covered Stent System RMV
 
Group B. Plastic Stents – PS Arm Per Investigator preference

Study Design	Prospective, multi-center, randomized
Planned Number of Subjects	164
Planned Number of Sites	Up to 15
Primary Endpoint	Stricture resolution at 24 months
Secondary Endpoints	
 1. Occurrence of adverse events related to the stent and/or the stent placement or removal procedures 2. Number of ERCP procedures through 24 months after initial stent placement 3. Ability to deploy the stent(s) in satisfactory position 4. Stent Removal: 
 • Ability to remove the stent(s) without serious stent removal related adverse events at each procedure involving removal of stent(s) (technical success at removal) or • Complete distal migration without serious stent removal related adverse events 5. Liver Function Tests (LFT's): 
 • Baseline LFTs compared to LFTs taken at time of original plastic stent placement for any subject with a prior plastic stent

	
 • LFT improvement at 1 month post-study treatment compared to baseline LFTs (and/or compared to LFTs taken at time of original plastic stent placement for any subject with a prior plastic stent) • LFTs at month 24 compared to LFTs at removal of last stent (applicable for subjects who had not been re-stented at time of month 24 visit) 
6. Health Economic Endpoints:
 
 • Number of outpatient procedures • Number of hospitalizations • Duration of hospitalizations • Length of procedures • Number of devices
Randomization	
Subjects will be randomized at the time of the procedure to a 1:1 ratio between Metal Stent Arm (Group A – MS) and Plastic Stent Arm (Group B – PS).

Follow-Up Schedule	
 • Baseline: Subject screening, enrollment, LFTs and symptoms. • Study Treatment Procedure: 
 ○ Group A (MS): Stent Placement ○ Group B (PS): Stent Placement: Two or more 8.5 Fr. or 10 Fr. PS whenever possible • 1 Month Follow-up: 
 ○ Group A (MS): LFTs and symptoms ○ Group B (PS): LFTs and symptoms • Stent Exchange Follow-up: 
 ○ Group A (MS): None ○ Group B (PS): Month 4 and Month 8 • Stent Removal: 
 ○ Group A (MS): Removal at Month 12, LFTs and symptoms ○ Group B (PS): Removal of last stents at Month 12, LFTs and symptoms • Post-Stent Removal Follow-Up 
 ○ Group A (MS): Month 24 – LFTs and symptoms ○ Group B (PS): Month 24 – LFTs and symptoms • Additional ERCP visits as needed 
Note: Recurrent strictures will be treated with a metal stent in Group A (MS) and with plastic stents in Group B (PS) – no cross-over. Re-stenting after the per-protocol 12 month stenting period will be considered primary endpoint failures. Follow-up, however, will continue until Month 24 after initial stent placement for all subjects, in order to assess all secondary endpoints in a comparative fashion for the

	MS and PS arms.
Key Inclusion Criteria	
 • Age 18 or older • Willing and able to comply with the study procedures and provide written informed consent to participate in the study • Chronic pancreatitis • Symptomatic bile duct stricture (defined by cholangitis or persistent jaundice for at least one month or cholestasis associated with at least 3 times normal alkaline phosphatase levels) documented at time of enrollment for naïve stricture or at the time of prior plastic stent placement in strictures that had one prior plastic stent inserted.¹² • Common bile duct stricture based on imaging assessment of dilatation of the common and/or intrahepatic bile ducts
Key Exclusion Criteria	
 • Biliary stricture of benign etiology other than chronic pancreatitis • Prior biliary metal stent or any plastic stenting other than one plastic stent of 10 Fr or less for 6 months or fewer • Developing obstructive biliary symptoms associated with an attack of acute pancreatitis • Biliary stricture of malignant etiology • Stricture within 2 cm of common bile duct bifurcation • Known bile duct fistula or leak • Subjects for whom endoscopic techniques are contraindicated • Known sensitivity to any components of the stent or delivery system • Symptomatic duodenal stenosis (with gastric stasis) • Participation in another investigational study within 90 days prior to consent • Investigator Discretion
Statistical Hypothesis	
A literature search of metal and plastic stenting for treatment of benign biliary strictures secondary to chronic pancreatitis yielded 4 articles representing 70 subjects treated with metal stenting (MS)^{1,9-11} and 3 articles representing 60 subjects treated with plastic stenting (PS)^{3,4,8}.
 
The following meta-analysis was conducted of the probability of stricture resolution:
 
 • Metal Stenting: A meta-analysis of the stricture resolution rate during the reported follow-up after initial stent placement yields a proportion

of 0.762 [95% CI: 0.593 – 0.895]^{1,9-11}.

- **Plastic Stenting:** A meta-analysis of the stricture resolution rate during the reported follow-up after initial stent placement yields a proportion of 0.611 [95% CI: 0.311 – 0.870]^{3,4,8}.

Statistical testing will be performed to determine if the rate of stricture resolution for the metal stent is non-inferior to the plastic stent group. The null hypothesis is that the stricture resolution rate is non-inferior in the Metal Stent Arm versus the Plastic Stent Arm:

$$H_0: \pi_{test} - \pi_{control} \geq \Delta \text{ (Inferior)}$$

$$H_a: \pi_{test} - \pi_{control} < \Delta \text{ (Non-inferior)}$$

where π_{test} and $\pi_{control}$ are the probabilities of having a stricture resolution in the metal stent arm and the plastic stent arm respectively, and Δ is defined as the non-inferiority margin.

The sample size was calculated for a one-sided 0.050 Farrington-Manning test using SAS 9.2®. If the P value from the Farrington-Manning test is <0.05 then the metal stent group will be considered non-inferior to the plastic stent group. The expected probability of stricture resolution in the metal stent arm and plastic stent arm is 66.0%, which was taken from the 95% CIs from the meta-analysis above. The non-inferiority margin (Δ) is 20%. Given these assumptions and a one-sided 5% significance level, $2 \times 74 = 148$ subjects will provide 80% power to reject the null hypothesis, that the metal stent group is inferior to the plastic stent group. To compensate for possible loss of subjects after enrollment and complete assessment of inclusion/exclusion criteria, an additional 10% of subjects will be enrolled, for a total of $2 \times 82 = 164$.

Table of Contents

1. Introduction	10
1.1. Introduction	10
1.2. Plastic Stents in Chronic Pancreatitis Strictures	10
1.3. Metal Stents in Chronic Pancreatitis Strictures.....	11
2. Device Description	11
3. Primary Objectives.....	12
4. Endpoints.....	12
4.1. Primary Endpoint	12
4.2. Secondary Endpoints.....	13
5. Design.....	14
5.1. Inclusion Criteria:.....	14
5.2. Exclusion Criteria:	14
6. Subject Accountability	15
6.1. Point of Enrollment	15
6.2. Withdrawal.....	15
7. Study Methods	15
7.1. Data Collection	15
7.2. Study Candidate Screening	17
7.3. Informed Consent.....	17
7.4. Study Visits	17
7.5. Study Completion	19
7.6. Source Documents	19
8. Statistical Considerations	19
8.1. Objective	19
8.2. Justification for Study Design and Sample Size Calculations	20
8.3. Eligibility of Subjects, Exclusions, and Missing Data.....	20
8.4. Analysis Populations.....	20
8.5. Analysis.....	21
8.6. Statistical Analysis.....	21
9. Data Management	22
9.1. Data Collection, Processing, and Review	22
9.2. Data Retention.....	22
10. Potential Risks and Benefits	22
10.1. Anticipated Adverse Device Effects	22
10.2. Risk Minimization Actions	24
10.3. Anticipated Benefits.....	24
10.4. Risk to Benefit Rationale	24
11. Safety Reporting	24
11.1. Definitions and Classification.....	24
11.2. Relationship to Study Device(s)	26
11.3. Investigator Reporting Requirements	27

11.4. Boston Scientific Device Deficiencies.....27
11.5. Reporting to Regulatory Authorities / IRBs / ECs / Investigators.....27
12. Amendments27
13. Deviations28
14. Device/Equipment Accountability28
15. Compliance.....28

1.1. Introduction

Benign strictures of the common bile duct may occur in approximately 3%-45% of subject with chronic pancreatitis.¹⁻⁵ Previously, surgery was typically performed for subjects with chronic pancreatitis, but is associated with high morbidity and mortality.³⁻⁵ Chronic pancreatitis subjects are also typically poor surgical candidates due to concomitant malnutrition, cirrhosis or portal hypertension.^{1,3,4} Non-surgical candidates will usually undergo endoscopic treatment with one or more multiple plastic stents placed, resulting in adequate short-term resolution of pancreatitis but associated with high occlusion and migration rates and poor long-term results.^{1,3}

Plastic stents, which are intended for temporary placement and are removable, have become standard of care for endoscopic treatment of benign strictures due to chronic pancreatitis.²⁻⁸ More recently, physicians are using self-expandable metal stents (SEMS) for treatment of and removal from such strictures due to the long-term patency, lower occlusion and obstruction rates, of metal stents compared to single or multiple plastic stents.^{1,9-11}

A summary of literature review below examines plastic stent placement and instances of metal stent placement for treatment of benign strictures in subjects with chronic pancreatitis.

1.2. Plastic Stents in Chronic Pancreatitis Strictures

A total of six studies (253 subjects) were analyzed for use of single or multiple plastic stents for benign biliary strictures; there were a total of 226 subjects with strictures due to chronic pancreatitis included in these studies.^{2-6,8} The average number of ERCP's (Endoscopic Retrograde Cholangiopancreatography) with stent exchanges per subject was 4.3 (range 1-17).^{3,5,8} Subjects with single plastic stents placed typically underwent stent exchange at 3-6 month intervals resulting in 1-4 exchanges per subject.^{3,5,6} These subjects also had a stent indwell time ranging from 10-15 months.^{3,4,6} Subjects with multiple plastic stents placed had stent indwell times ranging from 12-34 months.^{3,8}

Overall clinical success ranged from 24%-46% for subjects treated with a single plastic stent²⁻⁵, and 62%-92% for subjects treated with multiple plastic stents.^{3,8} In the subset of data available for chronic pancreatitis subjects treated with single plastic stents, success rates ranged from 7.7%-46%³⁻⁶ and one study specifying use of multiple plastic stents for chronic pancreatitis subjects had a reported success rate of 44%.⁸

Complications inclusive of all subjects in all studies of plastic stents included migration (10.2%-13%)^{3,4}, cholangitis (6.8%)⁸, bleeding (5.1%)⁴, occlusion (7.6%-46.5%)^{4,5}, pancreatitis (1.7%-3.4%)^{5,8}, liver abscess (1.7%)⁵, dislocation (1.7%)⁵, and clogging (92.3%).⁶

1.3. *Metal Stents in Chronic Pancreatitis Strictures*

A total of four studies (186 subjects) were analyzed for use of partially covered (n=99 subjects) or fully covered metal stents (n=87 subjects) for benign biliary strictures; there were a total of 71 subjects with strictures due to chronic pancreatitis included in these studies.^{1,9-11} Types of stents used included the partially covered Wallstent (Boston Scientific), uncovered Wallstent (Boston Scientific), Viabil, fully covered metal stent with an anchoring flap (M.I. Tech) and a fully covered metal stent with both ends flared (Standard Sci Tech). Behm et al¹ noted a range of 1-3 procedures per subject. Stent indwell times ranged from 6 months to 28 months.^{1,9,11} Success of metal stents in just chronic pancreatitis subjects ranged up to 95%.¹

Complications inclusive of all subjects in all studies of metal stents included migration (5%-16.2%)^{1,9,11}, bleeding (1%-5%)^{1,9,10}, pain (2%-5%)^{1,9,10}, pancreatitis (5%-13.9%)^{1,9,11}, cholangitis (4.6%-35%)¹¹ and occlusion (9.3%)¹¹.

2. Device Description

The WallFlex Biliary RX Fully Covered Stent System RMV is indicated for use in the palliative treatment of biliary strictures produced by malignant neoplasms, and for treatment of benign biliary strictures, per CE Mark. This clinical study will be conducted only in countries where this indication for use is cleared or approved per local regulatory requirements. Enrolled subjects will have benign biliary strictures secondary to chronic pancreatitis.

Study devices are labeled on the box and inner pouch and include information not limited to name of legal manufacturer, device name and dimensions, lot number, expiration date and investigational use statement. Device labeling will be provided in local language(s) as per national regulations.

For a detailed description of the WallFlex Biliary RX Fully Covered Stent System RMV, please reference the Directions for Use (DFU) included in each device package.

The DFU indicates stent placement for the following use: the palliative treatment of biliary strictures produced by malignant neoplasms, and for treatment of benign biliary strictures. Investigators should use the WallFlex Biliary RX Fully Covered Stent System RMV in accordance with the DFU.

Description	Delivery System Working Length (cm)	Stent Diameter (mm)	Stent Length (mm)
WallFlex Biliary RX Fully Covered Stent System RMV	194	8	60
WallFlex Biliary RX Fully Covered Stent System RMV	194	8	80
WallFlex Biliary RX Fully Covered Stent System RMV	194	10	40
WallFlex Biliary RX Fully Covered Stent System RMV	194	10	60
WallFlex Biliary RX Fully Covered Stent System RMV	194	10	80

3. Primary Objectives

To compare the use of Self Expanding Metal Stents (SEMS) to plastic stents for the treatment of benign biliary strictures secondary to chronic pancreatitis as it pertains to stricture resolution rates, complication rates and number of ERCP procedures during 24 months.

4. Endpoints

4.1. Primary Endpoint

4.1.1. Primary Endpoint Definition

Stricture resolution at 24 months.

Stricture resolution at 24 months is defined by the following two criteria being met:

- Absence of re-stenting after the per-protocol stenting period through the 24 month visit
- Absence of cholestasis at the 24 month visit, defined as alkaline phosphatase level not exceeding 2 times the level at completion of the per-protocol stenting period

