4.1.2. Primary Endpoint Failures

- Primary endpoint failures are 1) subjects who are re-stented during follow-up after the per-protocol stenting period and 2) subjects who have not been re-stented at month 24 but have alkaline phosphatase level exceeding 2 times the level at completion of the per-protocol stenting period.
- Subjects who experience early stent removal or complete distal stent migration without subsequent re-stenting will not be considered failures. If re-stenting occurs, but the

cumulative stenting period does not exceed 12 months, the subject remains eligible for primary endpoint assessment.

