4.1.3. Re-stenting

- Re-stenting after the per-protocol 12 month stenting period should only be considered if subjects meet initial criteria for stenting:
 - Symptomatic bile duct stricture (defined by cholangitis or persistent jaundice for at least one month or cholestasis associated with at least 3 times normal alkaline phosphatase level) documented at time of enrollment for naïve stricture or at the time of prior plastic stent placement in strictures that had one prior plastic stent inserted.¹²
 - Common bile duct stricture based on imaging assessment of dilatation of the common and/or intrahepatic bile ducts
- To minimize the risk of recurrent obstructive symptoms due to sludge or stones in the post-stent removal period, every attempt should be made to clear the bile duct of sludge and/or stone (i.e., balloon sweep and/or flushing).

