7.3 Rules and Definitions

Binary event rates (proportions) will be reported on a per patient basis.

The last follow-up date will be the latest of the following dates for each patient: date of an adverse event, index procedure date, follow-up visit date, any stent or ECRP procedure date, stent removal date, and device event date.

Stricture resolution at 24 months is defined by the following two criteria being met:

• Absence of re-stenting after the per-protocol stenting period through the 24 month visit

Version AA March 20, 2013 Boston Scientific WallFlex Biliary FC CP RCT SAP 90913894/Ver. AA Page 12 of 13 • Absence of cholestasis at the 24 month visit, defined as alkaline phosphatase level not exceeding 2 times the level at completion of the per-protocol stenting period

Primary endpoint failures are 1) subjects who are re-stented during follow-up after the per-protocol stenting period and 2) subjects who have not been re-stented at month 24 but have alkaline phosphatase level exceeding 2 times the level at completion of the per-protocol stenting period.

Subjects who experience early stent removal or complete distal stent migration without subsequent re-stenting will not be considered failures. If re-stenting occurs, but the cumulative stenting period does not exceed 12 months, the subject remains eligible for primary endpoint assessment.

For the final tables, two-sided exact tests will be done to test for differences between the two groups for removability and AEs. A one-sided non-inferiority Farrington-Manning test will be done to see if stricture resolution is non-inferior in the Metal group compared to the Plastic group. A two-sided student's t-test will done to test for differences between the two groups for the number of ERCP procedures done.

Version AA March 20, 2013 Boston Scientific WallFlex Biliary FC CP RCT SAP 90913894/Ver. AA Page 13 of 13

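### The 24-month stricture resolution rule can misclassify patients as written: early stent loss, the stenting clock, the unanchored alkaline phosphatase ratio and non-stent drainage need explicit scoring

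*Protocol*

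**What the plan says.** Protocol 4.1.1 requires two things for resolution. The first is "Absence of re-stenting after the per-protocol stenting period through the 24 month visit". The second is absence of cholestasis at month 24, "defined as alkaline phosphatase level not exceeding 2 times the level at completion of the per-protocol stenting period". SAP 7.3 repeats both.

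Protocol 4.1.2 and SAP 7.3 define two kinds of failure: re-stenting after the stenting period, and "subjects who have not been re-stented at month 24 but have alkaline phosphatase level exceeding 2 times" the end-of-stenting level. They add that "Subjects who experience early stent removal or complete distal stent migration without subsequent re-stenting will not be considered failures". A patient who is re-stented but whose "cumulative stenting period does not exceed 12 months, the subject remains eligible for primary endpoint assessment".

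The note under the Follow-Up Schedule in the Protocol Synopsis says "Re-stenting after the per-protocol 12 month stenting period will be considered primary endpoint failures". Protocol 4.1.3 says "Re-stenting after the per-protocol 12 month stenting period should only be considered if subjects meet initial criteria for stenting"; those criteria include duct dilatation on imaging. Protocol 7.4.8 says recurrent strictures must be treated with the allocated stent type.

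On timing, Table 1 puts stent removal at 330 to 360 days. Stent exchange visits are "Group B (PS): Month 4 and Month 8", and none in the metal arm. Liver function tests are drawn at month 1, months 11-12 and month 24, at any additional ERCP, and at month 4 or 8 if plastic stents are not replaced. Laboratory normal ranges are collected at baseline, at month 24 and at visits that result in re-stenting.

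**The concern.** This is the primary endpoint of a non-blinded non-inferiority trial. If the rules leave a patient's status open, someone must settle it later, possibly with outcomes in view. If the rules are followed literally, some patients get a status that does not match their stricture.

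Errors of equal share in both arms shrink the apparent difference, which makes a false claim of non-inferiority more likely. Errors concentrated in one arm can help or hurt either device. The schedule gives some reason to expect unequal handling: the plastic arm has ERCP visits at months 4 and 8, while the metal arm has no scheduled visit between month 1 and months 11-12.

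**Working it through.** **1. Early removal and migration.** 4.1.1 applies both criteria to every patient. The sentence on early removal and migration in 4.1.2 and SAP 7.3 says that such patients, if not re-stented, are not failures, without limiting this to the first criterion. Read literally, a patient whose stent migrated and whose month-24 alkaline phosphatase is three times the reference fails 4.1.1 but cannot be a failure under 4.1.2. The likely intent is that early removal alone is not failure; no sentence says so.

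Early draws exist (Table 1, 7.4.5, 7.4.8), but none is named as the endpoint reference. A metal stent that migrates without an ERCP has no scheduled draw until months 11-12. If the stricture has begun to recur by then, the reference is higher and the twofold limit looser.

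**2. The clock.** Take a stent lost at month 5 and a new stent in place from month 13 to month 18. Cumulative stenting is 5 + 5 = 10 months.

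| Reading of the 12-month period | Score |
|---|---|
| Calendar time (one reading of the Synopsis note and 4.1.3) | Failure: re-stented after month 12 |
| Cumulative time (4.1.2) | Still eligible: 10 months is within 12 |

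On a cumulative reading throughout, the three places agree; on a calendar reading they conflict. Two cases stay open under the cumulative sentence: re-stenting that starts within the allowance and runs past it, and a stent still in place at month 24. The second patient is not clearly in the first failure category, and the second category covers only patients not re-stented at month 24.

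**3. The ratio.** Failure requires month-24 value ÷ reference > 2.
- 3.0 ÷ 1.5 = 2.0, not above 2: resolved, although 3 times normal is the alkaline phosphatase level in the entry criteria (one of three alternative symptom criteria; duct dilatation is also required).
- 0.9 ÷ 0.4 = 2.25, above 2: failure, with a normal value.

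In general, a reference above 1.5 times normal lets a value above the 3-times entry level pass, and a reference below 0.5 times the upper limit lets a normal value fail. Table 1 schedules no draw between months 11-12 and month 24 and no imaging at month 24, so a rise first seen in the month-24 blood that stays within twofold counts as resolved.

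**4. Other drainage.** Both failure categories rest on re-stenting or alkaline phosphatase. A recurrence drained surgically or percutaneously meets neither if the month-24 value is low.

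**5. Size, for illustration.** Inputs from Protocol 8.1: 66% in each arm, margin 0.20, one-sided 0.05, 74 per arm, Farrington-Manning test, with the hypotheses read in their intended direction (null: metal at least 20 points worse).

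Plan's own figure first. With null variance at 46%/66%, s0 = √(0.46×0.54 + 0.66×0.34) = 0.688 and s1 = √(2×0.66×0.34) = 0.670. Then n = (1.645×0.688 + 0.842×0.670)² ÷ 0.20² = 71.8, so 72 per arm. Power at 74 is 81.1% by this formula and 83.2% by exact enumeration of the test. The stated 74 is reproduced, slightly on the safe side.

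Let m be the share of true failures scored as resolved. The apparent rate is p + (1 − p)m. Exact binomial enumeration at true 46% (metal) and 66% (plastic), 74 per arm:

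| Assumed m | Apparent metal / plastic | False non-inferiority |
|---|---|---|
| 0 | 46.0% / 66.0% | 5.7% |
| 1% both arms | 46.5% / 66.3% | 6.0% |
| 2% both arms | 47.1% / 66.7% | 6.3% |
| 5% both arms | 48.7% / 67.7% | 7.3% |
| 5% metal only | 48.7% / 66.0% | 10.8% |
| 5% plastic only | 46.0% / 67.7% | 3.6% |

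For successes scored as failures, take true rates of 66% in both arms. An assumed 5% share turns 66% into 0.66 × 0.95 = 62.7%. Power is 83% with no error, 83% with the error in both arms, 70% in metal only and 91% in plastic only.

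**The case against.** Several parts of the plan limit the problem, and they stand.

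- A reader might infer that the stenting period and the early reference are simply missing. They are not. The period is nominally 12 months with a removal window. Early draws are collected, and the secondary endpoint comparing month 24 with the removal of the last stent (4.2) points to a natural reference. What is missing is the clock and the designation.
- A reader might infer that late re-stenting goes unscored. Once the allowance is used up, new re-stenting is already failure under the Synopsis and 4.1.2. Only the two cases in step 2 stay open.
- A reader might infer that re-stenting is merely optional and so a weak backstop. 4.1.3 is permissive, but 7.4.8 says recurrent strictures must be treated. That wording may mainly fix the stent type, yet it makes re-stenting a real check that should catch many recurrences.
- A within-patient ratio may be a deliberate choice. That is a fair reason to keep it as primary.
- The migration rates in Protocol 1.2 and 1.3 might tempt a reader to put a size on the exemption. They do not support one: they cover all benign strictures, other stent models and migration in general rather than complete distal migration. The calculation would also need the less likely full-exemption reading and migration independent of failure.
- Surgical or percutaneous drainage is probably uncommon, given 1.1 and 7.4.8.

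None of this tells the analyst how to score the cases in the working.

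**Conclusion.** The point holds in this form: followed as written, the rule can misclassify the primary endpoint in both directions, and the SAP repeats the wording without repairing it. The firmest part is the text itself: the sentence on early removal and migration against the two-criteria definition, and the ratio examples, which need no assumption about frequency.

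The size is not known. Every misclassification share above is an assumption. Small equal errors matter little (5.7% to 6.0% or 6.3% at shares of 1% or 2%); unequal errors matter more and can go either way (10.8% or 3.6% at 5% in one arm). The inference that the rule favours the metal stent is not supported, because the documents give neither the frequency nor the net direction of error. It should be fixed because the scoring can be settled cheaply before outcomes are reviewed.

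**What to change.** For endpoint scoring only; patient care is unchanged.

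1. Reconcile the Synopsis note, Protocol 4.1.1 to 4.1.3 and SAP 7.3 with one definition of the stenting period. The sponsor chooses calendar or cumulative time before outcomes are reviewed. State how re-stenting that runs past the allowance, or is in place at month 24, is scored.
2. State that early removal or migration alone is not failure but that the alkaline phosphatase criterion still applies. Name the reference draw by one rule for both arms, for example the first liver function test at or after removal of the last stent or detected migration. Report the delay from stent loss to that draw by arm; the rule does not remove the delay in the metal arm, but the report shows it.
3. Score surgical or percutaneous biliary drainage for the stricture after the stenting period as failure.
4. Keep the twofold within-patient rule as primary. Pre-specify one sensitivity analysis using the month-24 normal range already collected: a value at or above the protocol's own 3-times entry level is failure, a value within the normal range is not, and all others follow the twofold rule. A normal range at the reference draw is needed only if the ratio itself is scaled to the upper limit of normal.

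The cost is wording in two documents, one extra table and a little analysis work. Reported resolution rates may be slightly lower.
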